Official Title:

A resorbable versus a non-resorbable bone substitute at immediate post-extractive single implants immediately loaded: a multicentre randomised controlled trial

Brief Title:

Resorbable vs non-resorbable bone substitute at immediate post-extractive single implants

NCT Number:

NCT07047131

Unique Protocol ID:

2301201902319

Date of the Document:

December 18, 2018

A resorbable versus a non-resorbable bone substitute at immediate post-extractive single implants immediately loaded: a multicentre randomised controlled trial

Introduction

A systematic review did not show statistically significant differences between immediate, immediate-delayed and delayed implant placement protocols in terms of performance due to the poor quality of the available clinical data and underpowered study designs(1). The use of bone substitute can improve aesthetics at post-extractive implants(2). Bone substitutes can be poorly resorbable (semi-degradable), meaning they simply preserve bone volume being integrated into newly-formed bone or can be rapidly resorbed (fully degradable) and replaced by new autogenous bone. It is currently unknown if one of the two mechanisms is preferable at immediate post-extractive implants.

Aims

To compare the effectiveness of a partly versus a fully resorbable bone substitute at immediate post-extractive single implants.

Study Design

Multicentre, single blind, randomised controlled trial of parallel group design where a partly resorbable bone substitute (Apatos) will be compared to a fully resorbable bone substitute (GTO) to fill bone-to implant gaps at immediate post-extractive implants.

Each patient will provide only one implant site. For patients with multiple teeth to be extracted, the operator will be free, at the screening visit, to select one future implant site to be included in the trial. The trial will have a duration of 5-year post-loading.

- Randomisation: using computer generated random numbers, centralized with sequentially sealed opaque envelopes provided by the study adviser ([name]).
- Allocation concealment: the operator will know about the type of graft to place at the implant to bone gap by opening a sealed envelope after the immediate implant has been placed and definitively included in the study.
- Blinding: independent and blind assessors will assess implant stability. Bone level changes, volumetric change and aesthetic evaluation will be done by a single blinded and independent assessor.

The principles outlined in the Declaration of Helsinki on clinical research involving human subjects will be adhered to. A written informed consent will be obtained for each patient. The study got the approval of the ethical committee King Juan Carlos University, Madrid, Spain

The trial will be reported according to the CONSORT statement for improving the quality of reports of parallel-group randomized trials (<http://www.consort-statement.org/>).

Inclusion criteria at screening

- Any patient requiring at least one single immediate post-extractive implant.
- At least 18 year old, able to understand and to sign an informed consent

- There must be sufficient bone to allow the placement of at least a 3.5 mm diameter and 8.5 mm long implant.
- After tooth extraction there must be a potential gap of at least 2 mm from the buccal inner bone plate and the implant surface.

Exclusion criteria at screening

- General contraindications to implant surgery.
- Immunosuppressed or immunocompromised patients.
- Patients irradiated in the head and/or neck.
- Uncontrolled diabetes.
- Pregnancy or lactation.
- Active periodontal disease
- Poor oral hygiene and motivation.
- Addiction to alcohol or drugs.
- Psychiatric problems and/or unrealistic expectations
- Patients with an acute infection (abscess) in the site intended for implant placement.
- Patients unable to commit to a 5-year follow-up.
- Patients treated or under treatment with intravenous amino-bisphosphonates.
- patients referred only for implant placement if follow-ups cannot be done at treatment centre.
- Patients participating in other studies, if the present protocol could not be fully adhered to. In case of doubts please contact [name] ([contact]).

Exclusion criteria after tooth extraction

- More than 4 mm in height of missing buccal wall, assessed using the highest peak of palatal wall as reference point.
- Less than 2 mm of space between the inner plate of the buccal bone and the implant surface.

Centre and main operator

King Juan Carlos University, Madrid, Spain

Treating surgeon: [name] [name] ([contact])

Masked local outcome assessor: [name] [name]

Study population and number of patients to be included

Prior to enrolment, all patients will be asked to sign an informed consent form to document that they understood the scope of the study (including procedures, follow-up evaluations, and any potential risks involved), were allowed an opportunity to ask questions pertaining to this study and were apprised of treatment alternatives. The study is open to qualifying patients without regard to sex or race.

Sample size

In this study, the primary comparison is the effectiveness of different bone substitutes in maintaining bone volumes, therefore, the sample size calculation will be based on bone volumes. To detect a difference of 5 mm³ in bone volume changes between the two bone substitutes (standard deviation of 6.96 mm³(3)) with a two-side 5% significance level and a power of 80%, a total sample size of 80 patients will be necessary, given an anticipated dropout rate of 20%. We can contribute with 50 patients (25 per group).

Outcome measures

Primary outcome variable

Volume changes of the volume changes of the peri-implant tissues will be evaluated by taking a limited view cone-beam computed tomography (CBTC) of the area of interest at implant placement, 1 and 5 years after loading.

Secondary outcome variables

Crown/implant failure: whether it will not be possible to place the crown because of implant failure or secondary to implant failure, and replacement of the crown for any reason. Implant failure is defined as implant mobility and/or any infection dictating implant removal and any mechanical complications rendering the implant unusable (e.g. implant fracture). The stability of each individual implant will be measured by the blinded outcome assessor manually by assessing the stability of the crown using the handles of two metallic instruments at 1 and 5 years after loading.

Biological and biomechanical complications: will be recorded and reported by study group. Examples of biological complications are: fistula, peri-implantitis. Examples of biomechanical complications are fracture of the metal screws, loosening of the crown, fracture of the ceramic lining.

Peri-implant marginal bone level changes: periapical digital radiographs will be made with the paralleling technique at implant placement, at 1 and 5 years of loading. In case of an unreadable radiograph, the radiograph must be made again. Peri-implant marginal bone levels will be measured using the Image J (National Institutes of Health, Bethesda, Maryland, USA) software. The software will be calibrated for every single image using the known implant length or, if the full implants is not visible on the radiograph, the implant diameter. Measurements of the mesial and distal bone crest level adjacent to each implant will be made to the nearest 0.01 mm. Reference points for the linear measurements will be: the coronal margin of the implant collar and the most coronal point of bone-to-implant contact. Bone levels will be measured at both mesial and distal sides and averaged. Bone level at single implants will be averaged at group level.

Aesthetic evaluation of the clinical pictures taken at delivery of the final crown (baseline), at 1- and 5-year follow-ups, on a computer screen by an independent blinded dentist. The pictures of the vestibular and occlusal aspects must include the two adjacent teeth. The aesthetic evaluation will be done following the pink aesthetic score (4).

Materials

Bone substitutes: the non-resorbable bone substitute is composed by porcine bone granules of cortical bone (Apatos Cortical®, OsteoBiol®, Tecnoss®, Giaveno, Italy) that will be stabilized by a thermogelling synthetic copolymer with type I and III collagen gel (TSV Gel®, OsteoBiol®, Tecnoss®). The resorbable bone substitute is composed by collagenated heterologous cortico-

cancellous porcine bone mix + TSV Gel (GTO®, OsteoBiol®, Tecnoss®). No other grafting material can be used.

- Implant types:

CM Alvim (Neodent, Straumann, Basel, Switzerland) tapered cylindrical threaded bone level implants with cone-morse connection. The implant is made of titanium grade 4 cold-worked and its surface was roughened using sandblasting and acid etching (NeoPoros surface). The operator will be free to choose implant lengths (8.0, 10.0, 11.5 and 13 mm long) and diameters (3.5 and 4.3 mm) according to clinical indications and his preferences.

- Definitive crowns: Screw-retained metal-ceramic crowns.

Clinical procedures

Screening visit (APPENDIX 1)

Potentially eligible patients are screened to establish their eligibility for the study. Please complete APPENDIX 1 (Patient eligibility CRF) and record the number and reason of non-included patients. Patients must be informed on the nature of the study and must sign an informed consent in their own language. Preoperative radiographs must be obtained for every included patient. Investigators are free to choose the most appropriate radiographic examination according to the clinical case (periapical, panoramic, CBCT scans, etc.).

After determining that the patient is qualified for the study, and informed consent has been given, a thorough oral examination will be performed to assess health status, identify oral pathologies that require treatment prior to implant therapy, and analyse available bone over vital structures and adjacent to remaining natural teeth. To record a visual baseline, preoperative intraoral facial and occlusal digital photographs will be made of each patient to document the condition of the dental anatomy and state of soft tissue health.

Patients will be categorised into: 1) non-smokers; 2) moderate smokers (up to 10 cigarettes/day); 3) heavy smokers (more than 10 cigarettes/day), according to what they declare.

OPERATIVE PROCEDURES

Please complete APPENDIX 2 (Surgical and prosthetic CRF)

Prophylactic therapy: Scaling 2-3 days before surgery.

Amoxicillin 2 g one hour prior to tooth extraction and implant placement. Patients allergic to penicillin will be prescribed clindamycin 600 mg 1 hour prior to the interventions. Patients will rinse with chlorhexidine mouthwash 0.2% for 1 minute prior to the intervention.

Local anaesthesia: Articain with adrenaline 1:100.000.

Tooth extraction: Tooth extractions should be performed as atraumatically as possible attempting to preserve the buccal alveolar bone. Extraction sockets must be carefully cleaned from any remains of granulation tissue.

Immediate post-extractive implant installation technique: Drills with increasing diameters will be used to prepare the implant site as suggested by the manufacturers.

Implant sites will be underprepared of at least 1 twist drill size and implants will be inserted with the motor set at a 35 Ncm torque, to ensure adequate implant primary stability.

The choice of the implant diameter and length will be recorded. Implants will be placed slightly subcrestally, about 2 mm below the most apical bone peak, and slightly palatally. Cover screws will be placed. If there is sufficient buccal wall (no more than 4 mm of bone loss and the gap between the buccal wall and the implant is of at least 2 mm, the patient will be finally included in the study.

Disclosure of the randomised allocation

Once the implant has been placed and whether there is sufficient buccal bone (no more than 4 mm of buccal bone loss using the highest peak of palatal wall as reference point) and in the presence of an implant to buccal bone gap of at least 2 mm, the operator will know whether the bone to implant gap will be filled with a semi- or a fully-degradable bone substitute by opening the corresponding sealed envelope. It is absolutely forbidden to open the envelope containing the random code before. The surgeon will write on the Surgical and prosthetic CRF (APPENDIX 2) the patient sequential number contained in the envelope and to which of the two groups the patient is allocated.

Any residual gap between the implant surface and the socket walls will be filled with the bone substitute type as decided by the random allocation procedure. No other type of bone grafting material is allowed. Baseline periapical and limited view CBCT radiographs must be taken. If peri-implant marginal bone levels are difficult to be assessed, a second periapical radiograph will be taken. Implants achieving a torque of at least 35 Ncm will be loaded immediately while those implants placed with less than 35 Ncm will be covered with a standard (0.5 mm thick) collagen membrane of equine pericardium origin (Evolution®, OsteoBiol®, Tecnooss®) and submerged unloaded for 4 months. After 4 months they will be rehabilitated following the same procedures as all other study implants.

Post-surgical instructions and follow-ups

- Postoperative antibiotics will be prescribed: Amoxicillin 1 g 3 times a day for 6 days. Patients allergic to penicillin will be prescribed clindamycin 300 mg thrice a day for 6 days.
- Ibuprofen 400 mg will be prescribed to be taken 2 to 4 times per day, but patients will be instructed not to take it in absence of pain.
- Chlorhexidine mouthwash 0.2% for 1 minute twice a day for 2 weeks.

Prosthetic procedures

An impression with the pick-up impression copings will be made with a polyether material. Within 2 weeks, a definitive metal-ceramic screw-retained crown will be delivered on definitive titanium abutments.

- Periapical radiographs must be made. If the peri-implant marginal bone levels are not readable a second radiograph must be taken.
- Buccal and occlusal pictures of the implant including one adjacent tooth per side must be made.

1 year after loading (APPENDIX 2):

- Crowns will be manually tested for stability.
- Periapical radiographs must be made. If the peri-implant marginal bone levels are not readable a second radiograph must be taken.
- Buccal and occlusal pictures of the implant including one adjacent tooth per side must be made.
- A limited view CBCT of the study implant must be taken.

5 years after loading (APPENDIX 2):

- Crowns will be manually tested for stability.
- Periapical radiographs must be made. If the peri-implant marginal bone levels are not readable a second radiograph must be taken.
- Buccal and occlusal pictures of the implant including 1 adjacent tooth per side must be made.
- A limited view CBCT of the study implant must be taken.

All patients will be recalled every 6 months for professional maintenance. If necessary, the number of maintenance visits can be increased.

In case of suspected implant loss, peri-implantitis, fistula, etc., observed during any of the scheduled visit or during an emergency visit, intraoral radiographs and clinical pictures must be taken and the “Complications, protocol deviation and drop-out CRF” (APPENDIX 3) should be filled in.

Time

Day 1	photos/extraction/implant placement/patient inclusion/photos/group allocation/augmentation/impression/rx/CBCT
Within week 2	definitive crown delivery/photos
1 year after loading	implant stability/impressions/rx/CBCT/photos/maintenance
5 years after loading	implant stability/impressions/rx/CBCT/photos/maintenance

Drop-outs

All drop-outs should be reported and the reason for dropping out should be investigated and reported per study group. No included patient can be excluded for any reasons by the clinical investigators.

Statistical analysis

All data analysis will be carried out according to a pre-established analysis plan by a dentist with expertise in statistics blinded to group allocation. Descriptive statistics will be performed using mean and standard deviation for quantitative data and frequency and percentage for qualitative data. All-important harms or unintended effects in each group will be reported. The statistical unit of the analysis will be the patient. The primary outcome variable will be volume changes between baseline and 1- and 5-year after augmentation.

For volumetric analysis, an intra-rater agreement study will be performed on the operator to test his reliability. A set of 20 volumetric changes will be evaluated twice with a two-week interval between the measurements. The operator will be considered reliable if the intraclass coefficient of correlation is greater than 0.75.

A comparison of the baseline characteristics between groups will be presented. Differences in the proportion of dichotomous outcomes (e.g. prosthesis and implant failures, complications) will be compared between the groups using a chi-square test. Mean differences between groups for continuous outcomes (e.g. peri-implant marginal bone level changes, PES scores and volumetric analysis) will be compared using an independent sample t-test for pairwise comparisons. Comparisons between each time points and the baseline measurements will be made by paired t-tests, to detect any changes in marginal peri-implant bone levels for each study group.

All statistical comparisons will be conducted at the 0.05 level of significance and estimate, standard error, 95% confidence intervals and P-value will be reported for each term of the models.

In the case of early implant failure or complication the volumetric change will be measured anyway.

The statistical analysis will be intention-to-treat and deviation from the protocol will be considered according to the randomization scheme: all participants will be included in the analysis regardless of adherence to the protocol. In any case, if large deviations from the protocol are generated, a sensitivity per-protocol analysis will be performed.

Administrative procedures and data management

The centre is required to keep complete clinical records and study forms for all patients included in the study. Case report forms (CRFs) should be filled in at the time of data collection. Complete CRFs, and disks containing the digitized clinical pictures and radiographs should be attached to the study folder of each patient.

All data requested for this study will be collected using paper CRFs. The CRFs will be stored in a secure locked place to which only the principal investigator and the responsible for data collection will have access to. Data will also be accessible to [name] and Tecnoss for monitoring purpose at their discretion. After completion of the various follow-up points (delivery of the final crowns, 1 and 5 years after loading) copies of all the CRFs will be sent to [name] who will check the data and store them in a computer secured with a password known to him only. Data will be processed by a dentist with expertise in statistics (to be decided) under supervision of [name]. Patient identity will be protected and known only to the study participants listed in the present protocol.

Protocol amendments and violations

Amendments to this protocol may be necessary and violations to the protocol are likely to occur. Any violation of the protocol should be reported in the “Complications, protocol deviation and drop-out CRF” (APPENDIX 3). In case of problems please contact the study coordinator without delay.

Case report forms (CRFs)

- Patient informed consent form
- Patient eligibility CRF (APPENDIX 1)
- Surgical, prosthetic and follow-up CRF (APPENDIX 2)
- Complications, protocol deviation and drop-out CRF (APPENDIX 3)

REFERENCES

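### The allocated group is written in clear on Appendix 2, the form also used at the masked 1- and 5-year visits, and no step shields that entry while the form is in use

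*Protocol*

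**What the plan says.** Four parts of the protocol bear on this point.

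- **Where the group is recorded.** Under Disclosure of the randomised allocation, the surgeon is to write on Appendix 2 "the patient sequential number contained in the envelope and to which of the two groups the patient is allocated". What is entered is the group itself, not a masked code.
- **Where that form is used again.** The 1-year visit is headed "1 year after loading (APPENDIX 2"), and the 5-year visit carries the same reference. The list under Case report forms (CRFs) has a single entry, "Surgical, prosthetic and follow-up CRF (APPENDIX 2").
- **How the forms are kept.** Under Administrative procedures and data management, the forms are paper and are completed when the data are collected. Completed forms and "disks containing the digitized clinical pictures and radiographs should be attached to the study folder of each patient". The forms are locked away, with access for the principal investigator and whoever is in charge of data collection. A named central person and the manufacturer may also see the data for monitoring.
- **What blinding is promised.** Study Design promises blind, independent assessors for implant stability, and one blinded, independent assessor for bone level, volume and aesthetics. Secondary outcome variables repeats it for stability: "The stability of each individual implant will be measured by the blinded outcome assessor manually", at 1 and 5 years.

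**The concern.** The surgeon has to know the group, so masked assessment is the protocol's stated safeguard against bias in measurement. The outcomes need that safeguard because they depend on judgement: CBCT volume, reference points on radiographs, an aesthetic score from photographs, and stability felt through two instrument handles. One person reads all the image outcomes, so a leaning in that reader would not be averaged out across readers.

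The protocol guards the allocation carefully before it is disclosed, with sealed opaque envelopes and an explicit ban on early opening. Once the envelope is open, the group goes in clear onto a form that returns at the two visits where the masked stability assessment takes place. Nothing comparable protects it from then on.

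**Working it through.** The protocol gives no figure on this point to reproduce, and the sample size does not enter. The check is to follow Appendix 2 through the document and see who writes on it, holds it and could see it.

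1. **Entry.** At surgery the surgeon writes the sequential number and the group on Appendix 2 (Disclosure of the randomised allocation).

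2. **One form or two?** The operative sections call Appendix 2 the surgical and prosthetic form, while the CRF list adds follow-up to its name. The appendix number is the same in every place, and the list has no other follow-up form. The text therefore describes one form for surgery, crown delivery and follow-up. The appendix itself is not available, so whether the allocation entry shares a page with the follow-up entries is unknown.

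3. **Use at 1 and 5 years.** Both visits refer to Appendix 2, and crown stability is tested at both. Secondary outcome variables assigns that test to the blinded assessor. Forms are completed when the data are collected, but the person who completes them is not named. The section Centre and main operator lists two roles, the treating surgeon and a masked local outcome assessor. That leaves three possibilities:
   - The assessor completes the form. The form in hand then carries the group, unless the pages are separate or the entry is covered.
   - The surgeon completes it. The assessor can stay masked, but an unmasked person writes down the masked finding.
   - A third person completes it. The masking can hold, but the protocol names nobody for this.

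4. **Storage.** Locked storage controls who can fetch the form. It does not control what can be seen once the form is out for a visit. The protocol also does not say whether the person in charge of data collection may be the masked assessor.

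5. **Images.** Disks and completed forms go into the same patient folder. The aesthetic scoring is done on a computer screen. The protocol does not say whether the reader works from the folder or receives coded images taken from it. Exposure is possible, but it needs an extra step that the text does not describe.

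6. **Safeguard.** No section has the allocation entry detached, covered or withheld, and none says that assessors receive material bearing only the sequential number.

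Steps 1 to 3 establish a route to the stability assessor, and step 5 a weaker one to the image reader. Step 6 shows that neither is closed by a stated procedure.

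**The case against.** The strongest reply is that following the protocol as written unblinds nobody. It never says that an assessor completes, holds or reads Appendix 2. Stored forms are locked, and no assessor is named among those with access. The masked assessor is listed separately from the surgeon, and someone else could record the stability finding. Appendix 2 may have separate pages for each visit; sending copies after each follow-up point would fit that. Sharing a folder does not show that the image reader is handed the form.

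All of this stands against the stronger reading that blinding fails when the plan is followed. It does not remove the narrower point: the protocol directs that the group be written on the form used at the masked visits, and states nothing that shields it there.

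Two further inferences are tempting, and the text supports neither:

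- **The analyst is unblinded.** After each follow-up point "copies of all the CRFs will be sent to" a central person, who checks and stores the data. Analysis is then done "by a dentist with expertise in statistics blinded to group allocation". A dataset with coded groups is compatible with both statements, and that coding may properly be left to the analysis plan.
- **The manufacturer's access breaks the blind.** The protocol never says that the manufacturer or the central person is blinded, so their seeing the group contradicts no promise.

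Nor is assessor masking the trial's only protection against bias. Randomisation, concealment until the implant is placed and the patient finally included, and intention-to-treat analysis are all specified.

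**Conclusion.** The point holds as an avoidable risk to a promised safeguard, and not as a demonstrated failure of blinding. It rests on what the text states: the group in clear on Appendix 2, the same appendix at 1 and 5 years, filing together with the images, and no stated step that separates or masks the entry.

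The risk is clearest for manual stability, a secondary outcome. It is weaker for the image outcomes, which include the primary volume outcome, because that route depends on how images reach the reader. If Appendix 2 in fact has detachable visit pages, or if a third person records the findings, much of the risk disappears; the protocol should then say so.

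No size can be attached. The documents give no basis for how far a reader who knew the group would lean, so any figure would rest on an invented value. The case for the change is that it costs almost nothing and protects what the protocol already promises.

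**What to change.** Two edits to the protocol:

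- **Disclosure of the randomised allocation.** Have the surgeon record the group on a separate one-page allocation sheet, kept with the opened envelope and outside the patient folder. Only the sequential number is entered on Appendix 2. If Appendix 2 has a field that names the graft product, move that to the allocation sheet as well, since it gives the same information.
- **Administrative procedures and data management.** State that Appendix 2 and the images given to assessors carry only the patient's sequential number, and that assessors have no access to the allocation sheet.

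The cost is one more sheet to file for each patient. No extra patients, visits or staff are needed.

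### Implants below 35 Ncm stay in the trial, submerged and unloaded for 4 months, although the official title and visit schedule describe only immediate loading and the stated primary test ignores loading category

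*Protocol*

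**What the plan says.** - **Title and aim.** The official title describes a trial "at immediate post-extractive single implants immediately loaded". The brief title does not mention loading, and neither does the Aims section: "To compare the effectiveness of a partly versus a fully resorbable bone substitute at immediate post-extractive single implants".
- **Insertion.** Under the installation technique, "implants will be inserted with the motor set at a 35 Ncm torque".
- **Inclusion.** Final inclusion depends on the buccal wall and the width of the gap. Torque appears in no inclusion or exclusion list.
- **Order of events.** The implant is placed, the patient is definitively included, the envelope is opened and the gap is grafted. The section on disclosure of the allocation then gives the loading rule.
- **Two pathways.** The first is stated as "Implants achieving a torque of at least 35 Ncm will be loaded immediately". For the remainder, the same section provides that "those implants placed with less than 35 Ncm will be covered with a standard (0.5 mm thick) collagen membrane", and it keeps them submerged for 4 months without load. On what follows it says: "After 4 months they will be rehabilitated following the same procedures as all other study implants".
- **Schedule.** The time table lists one route only, with the definitive crown within week 2.
- **Analysis.** Under Statistical analysis, continuous outcomes, volume change among them, "will be compared using an independent sample t-test for pairwise comparisons". All participants are included by intention to treat. No loading factor is named.
- **Records.** The text says that the chosen implant diameter and length are recorded. It does not say so for torque.

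**The concern.** Part of the randomised population will, by protocol, never be immediately loaded, so the title and time table do not describe everyone who is analysed. The primary outcome is volume change around the grafted gap. Submerged sites differ from the others in coverage and in loading during the first 4 months. If that affects volume, an analysis that ignores it carries avoidable noise.

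There is also a question of sequence. Torque is reached at insertion, before the allocation is known, but the load-or-submerge step is described after the operator has opened the envelope. If torque is not written down first, the plan has no documented safeguard against knowledge of the graft colouring a borderline classification. A factor fixed after disclosure would also be less safe to adjust for.

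**Working it through.** **Inputs from the Protocol (Sample size):** difference 5 mm³, SD 6.96 mm³, two-sided 5% level, 80% power, 80 patients in total, 20% dropout. The 25 per group in that section is one centre's contribution, so the planned trial has 40 per arm.

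**Assumed:** share f of implants below 35 Ncm, 10 to 30%; difference B in mean volume change between submerged and immediately loaded sites, 3.5, 7 or 10 mm³, equal in both arms. The Protocol gives neither.

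**1. The plan's own figure.** A two-sample t-test with effect 5/6.96 = 0.718 needs 31.4, so 32 per arm. Then 64/(1 − 0.20) = 80. The stated total reproduces, and power at 32 evaluable per arm is 81%.

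**2. Bias.** The torque rule is the same in both arms, and torque arises before disclosure. The expected submerged share is therefore equal in the two arms, and B cancels from the expected difference between grafts. This relies on the category following the torque actually reached.

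**3. Precision when pathways are pooled without adjustment.** If 6.96 is the SD within a pathway, the pooled variance is 6.96² + f(1 − f)B². At f = 20%, f(1 − f) = 0.16:

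| B (mm³) | Variance | SD | Power, 32 per arm |
|---|---|---|---|
| 0 | 48.44 | 6.96 | 81% |
| 3.5 | 48.44 + 1.96 = 50.40 | 7.10 | 79% |
| 7 | 48.44 + 7.84 = 56.28 | 7.50 | 75% |
| 10 | 48.44 + 16.00 = 64.44 | 8.03 | 69% |

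Over f = 10%, 20% and 30%, power is 80, 79 and 79% for B = 3.5, and 77, 75 and 73% for B = 7. For B = 10 it is 74, 69 and 66% (variances 57.44, 64.44 and 69.44).

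**4. The same effect seen as chance imbalance.** The between-arm difference in submerged share has SD √(2 × 0.16/32) = 0.10, or 10 percentage points. Multiplied by B, this moves the estimate with an SD of 0.35, 0.7 or 1.0 mm³. For a single case, four more submerged implants in one arm at B = 10 shift the estimate by 4/32 × 10 = 1.25 mm³, or 4/40 × 10 = 1.0 mm³ with all 40 per arm. This restates step 3 and is not an additional loss.

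**5. What a factor does.** If B is common to both arms, a factor for loading category returns the residual SD to 6.96 and power to about 81%, with residual degrees of freedom going from 62 to 61.

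**6. What restriction does.** Analysing only immediately loaded implants at f = 20% leaves 32 × 0.8 = 25.6 per arm and about 71% power. That is worse than pooling unadjusted at B = 3.5 or 7, so the subset can only be supportive.

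**The case against.** The strongest reply is that the trial compares grafts, not loading protocols. The Aims section and brief title are silent on loading, the rule applies equally to both arms, and keeping every implant is an openly stated pragmatic choice. That stands. A reader might infer that the result cannot answer the trial's question, or that pooling biases it. The documents support neither: the question in the Aims section covers both pathways, and the contrast is unbiased in expectation.

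A second reply is that a fixed torque threshold leaves the operator no stated discretion, and that the surgical case report form, which is not shown, may already hold torque. Both parts are fair. Nothing suggests misclassification, and the point is only that the text does not require the value to be recorded before disclosure.

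A third is that covariates belong in an analysis plan that is not shown. The Protocol does refer to a pre-established plan, so the absence of a factor is not an omission in itself. But the Protocol names the primary test, and that named test can be improved at little cost.

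Finally, the losses rest on assumed values. A 10 mm³ difference is twice the design effect, and the documents do not say whether 6.96 already contains this variation. If it does, the unadjusted test keeps its 81%, and adjustment would be a gain rather than a repair.

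**Conclusion.** The point holds as a mismatch of description and a modest, avoidable loss of precision. The title and time table describe immediate loading only, the allocation section provides two pathways, and the named test pools them without a loading term. At 32 evaluable per arm and an assumed 20% submerged share, power goes from 81% to about 79%, 75% or 69% for assumed differences of 3.5, 7 or 10 mm³. These figures assume that the difference is the same in both arms and that 6.96 mm³ is a within-pathway SD.

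The randomised comparison remains valid for immediate post-extractive implants under either pathway, as long as torque settles the category before the graft is known. This is a cheap improvement, not a flaw that undermines the trial. No view is taken on which loading rule is clinically right.

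**What to change.** 1. Require insertion torque and the resulting loading category to be written on the surgical case report form before the envelope is opened.
2. Include that pre-randomisation category (immediate, or submerged with membrane) as a factor in the primary comparison of volume change, and keep all randomised patients.
3. Reconcile the official title and the time table with the two pathways. Word the conclusion for immediate implants with immediate or delayed loading, and report the graft difference in the immediately loaded subset as supportive only.

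The cost is one line on a form, one degree of freedom, one table and some rewording. The clinical loading rule stays as it is.
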